RESEARCH PROTOCOL

UNIVERSITAS
INDONESIA

Veritas, Probitas, Iustitia
— EST. 1849 —

IMPACT OF OBESITY ON SEVERITY OF ESOPHAGEAL REFLUX IN GASTROESOPHAGEAL REFLUX DISEASE MEASURED BY PH- METER IMPEDANCE

INVESTIGATORS:

Principal : [name]

Others : [name] [name], SpPD, K-GEH, Prof. dr. [name], SpPD, K-GEH, PhD, dr. [name], Sp.PD

FACULTY OF MEDICINE
UNIVERSITY OF INDONESIA

I. BACKGROUND

Gastroesophageal reflux disease (GERD), a prevalent communal health problem, is defined as a condition wherein the contents of the stomach are refluxed into the esophagus, resulting in symptoms and/or complications [1]. Although rarely the cause of death, GERD is associated with increased morbidity and negatively affects the quality of life [2]. Epidemiological studies show that the prevalence of GERD in Western countries is approximately 20%, with a 4% annual increase in prevalence [1,3]. Based on the studies in several Asian countries, its prevalence in Asia appears to be lower than that in the United States or Europe, but the prevalence has nonetheless increased in the past few decades [4-6]. In a hospital-based study, [name] et al. (2003) reported an increase in the prevalence of esophagitis from 5.7% in 1997 to 25.18% in 2002 [7]. Lelosutan et al. (2001) reported that GERD was diagnosed in 22.8% of 127 patients, based on upper GI endoscopy [8]. Recent data from 2016 also showed the prevalence of GERD among medical doctors to be 27.4% in Indonesian doctors [9].

The National Health and Nutrition Examination Survey (USA) reported that among 20–74-year-old adults, the prevalence of obesity increased from 15.0% in 1976–1980 to 32.9% in 2003–2004. It is estimated that by 2020, 77.6% of men will be overweight, and 40.2% will be obese; in addition, 71.1% of women will be overweight, and 43.3% will be obese [9]. Although the association between GERD and obesity remains unclear, they are believed to be positively related [10]. [name] et al. reported that obese patients have a higher risk of GERD, with the causative factors being higher dietary intake, decreased physical activity, and genetic predisposition. However, to the best of our knowledge, no studies have specifically examined the relationship between obesity and severity of esophageal reflux in GERD patients [11].

Currently, the GERD questionnaire (GerdQ) is used as a screening tool for GERD, with a specificity and sensitivity of 64.6% and 71.4%, respectively [12]. In Indonesia, GERD is diagnosed based on symptoms assessed using the GerdQ and upper gastrointestinal endoscopy. Unfortunately, because approximately 70% of GERD patients do not show esophageal damage during upper gastrointestinal endoscopy, the diagnosis of GERD requires methods that provide greater precision, one such method being the multichannel intraluminal impedance pH-meter (MII-pH) test, an esophageal manometric method that detects the incidence of reflux for 24 h and can be used to measure the strength of esophageal acidity; the latter represents severity of esophageal reflux. MII-pH results are expressed as the DeMeester or pH composite score [12,13].

II. OBJECTIVE AND HYPOTHESIS

A. General Objective

To ascertain if there is an association between obesity and severity of esophageal reflux, GERD must be diagnosed with greater precision and accuracy.

B. Specific Objective

1. To measure the acid exposure time obese patients and normal BMI patients.
2. To record the number of observed hiatal hernia in obese patients and normal BMI patients.
3. To record the number of erosive esophagitis in obese patients and normal BMI patients.

C. Hypothesis

1. Obese patients had higher DeMeester score and acid exposure time compared to normal BMI patient.
2. Obese patient had a higher number of observed hiatal hernia.
3. Obese patient had a higher number of observed erosive esophagitis.

III. METHODS

A. Study Design

This study is a cross sectional study.

B. Time and Place

A cross-sectional study involving 98 GERD patients was conducted between January and October 2017 at the Department of Internal Medicine, Cipto Mangunkusumo Hospital (Jakarta, Indonesia).

C. Study Population

1. **Targeted population:** Adult patients with GERD

2. **Sample:** Adult patients with GERD in in Cipto Mangunkusumo Hospital, Jakarta.

3. Inclusion Criteria

- Adults, aged 18–60 years;
- Normal BMI (18.5–23.5 kg/m²) or obese BMI (\geq 25 kg/m²); the BMI cut-off was based on the criteria for the Asia-Pacific population
- Fulfill GERD criteria assessed using GerdQ
- Gave undergone upper gastrointestinal tract endoscopy
- Willing to participate by providing written informed consent.

4. Exclusion Criteria

- Severe blood clotting disorders, severe heart disease, persistent asthma, decompensated liver cirrhosis, and chronic kidney disease.
- Prescribed benzodiazepine drugs, tricyclic antidepressants, dihydropyridine calcium channel blockers, adrenergic alpha inhibitors, beta blockers, or nonsteroidal anti-inflammatory drugs.
- Diagnosed with psychological disorders.

5. **Drop Out Criteria:** Patients who have signed the informed consent but wish to stop participating before completed the study.

D. Study Procedure

Patients diagnosed with Barrett's esophagus, peptic ulcers, or severe NSAID gastropathy; those suffering from hematemesis, melena, gastric cancer, esophageal cancer, pharyngeal obstruction, or upper esophagus on endoscopic examination; those in whom MII-pH meter could not be attached; uncooperative patients; and those unable to understand or follow instructions were also excluded from this study.

From 110 subjects who met the inclusion criteria, we excluded 12 subjects due to the above reasons. All 98 eligible subjects (59 female and 39 male) were recruited, provided anamnesis, and underwent a physical examination that included measurement of their weight and height.

The GerdQ was administered to all subjects, and those with a score of ≥ 8 points were diagnosed as having GERD. All patients with diagnosed GERD underwent upper gastrointestinal endoscopy, during which hiatal hernia and erosive esophagitis were also evaluated. The patients with diagnosed GERD also underwent MII-pH examination for 24 h for the quantification of the DeMeester score.

MMI-pH

MII-pH test was performed after an 8-h fast and after being PPI-free for seven days. The MII-pH system comprises a portable data storage unit and a catheter with one pH electrode and eight impedance electrodes at positions 3, 5, 7, 9, 15, and 17 cm from the tip. The electrode was placed 5 cm above the LES boundary, as determined by manometry. The patients were asked to press an event marker button on the data storage unit when they experienced symptoms and subsequently record information on the timing of symptoms, start and finish time, and changes in body position (lying or upright) in a diary. They were also required to at least eat three meals a day and were asked to maintain normal activity. Data were recorded on a 256 MB compact flash card, downloaded onto a computer for analysis using semi-automated software, and manually verified.

E. Ethics

The study protocol was approved by Health Research Ethics Committee, Faculty of Medicine, Universitas Indonesia-Cipto Mangunkusumo Hospital (No. 719/UN2.F1/ETIK/2017).

IV. STUDY ANALYTICAL PLAN

The data were analyzed using the STATA program (StataCorp). Categorical variables are presented as frequency and percentage, whereas numerical variables are presented as mean (with standard deviation) for normally distributed data. The median (with minimum and maximum range) is used for non- normally distributed data. Dichotomous categorical variables were analyzed using the chi-square test. Normality was evaluated using ..., and non-normal data was subjected to bivariate analysis using the Mann–Whitney U-test to compare the DeMeester score between the two groups. Statistical significance was set at $p < 0.05$, with 95% confidential interval (CI)..

REFERENCES

3. El-Serag H B 2007 Time trends of gastroesophageal reflux disease: a systematic review. *Clin Gastroenterol Hepatol.* 5 17-26
7. [name] A F, Abdullah M, Rani A A 2003 Prevalence of reflux esophagitis, Barrett's esophagus and esophageal cancer in Indonesian people evaluation by endoscopy. *Canc Res Treat.* 5 83
9. [name] A F, Hapsari C P, and Makmun D 2016 The prevalence and risk factors of GERD among Indonesian medical doctors. *Makara J Health Res.* 20 35-40

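### No masking to BMI group is described for the manual verification of the pH recordings, so the DeMeester score and acid exposure time are open to reader-expectation bias of unknown size

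*Combined protocol and SAP*

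**What the plan says.** Section III.D (Study Procedure) states that patients diagnosed with GERD "underwent MII-pH examination for 24 h for the quantification of the DeMeester score". Its subsection on the pH-impedance test describes the data path: "Data were recorded on a 256 MB compact flash card, downloaded onto a computer", followed by "analysis using semi-automated software, and manually verified". It does not say who verifies, under what rules, how many readers there are, or what they know about the patient.

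The comparison groups are set at entry in Section III.C: "Normal BMI (18.5–23.5 kg/m²) or obese BMI" of at least 25 kg/m². Section III.D adds that subjects "underwent a physical examination that included measurement of their weight and height", and describes this before the pH test.

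The expected direction is in Section II.C: "Obese patients had higher DeMeester score and acid exposure time compared to normal BMI patient". Section IV names one outcome only, in its plan to use the "Mann–Whitney U-test to compare the DeMeester score between the two groups".

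No section mentions masking, blinding, coded files or independent reading.

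**The concern.** Four features come together. A person has a hand in the measurement, the study knows the comparison group before the measurement is read, the hypothesis says which group should score higher, and no safeguard separates the reader from the group. If verification leaves any room for judgement, a reader who knows the group and expects obese patients to reflux more may resolve doubtful cases differently in the two groups.

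Such an error would push the result towards Hypothesis 1. Random reading error adds noise and is reflected in the standard error. A differential shift is not: it looks like a real group difference, the p-value gives no sign of it, and a larger sample only makes it more likely to reach significance.

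**Working it through.** **Is there a human step on the outcome?** Yes. Section III.D describes semi-automated software followed by manual verification. It does not say which outputs a reader may change or how often that happens.

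**Is the affected outcome important?** No outcome is labelled primary. Specific Objective 1 names acid exposure time, Hypothesis 1 names both the DeMeester score and acid exposure time, and Section IV names only the DeMeester score. Calling these the leading outcomes is an inference from those places.

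**Could the group be known at reading?** Yes. BMI group is an inclusion criterion, and weight and height are measured at the study examination.

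**Is any protection described?** None was found in any section.

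**How much could it matter?** The plan gives no figure to reproduce: no sample-size calculation, SD, group split, reader agreement or share of recordings edited. Only the counts can be checked, and they agree: 110 − 12 = 98 and 59 + 39 = 98. What follows shows what an assumed shift would do. It does not estimate what happened.

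Inputs from the document: total of 98 subjects (Section III.D) and significance level 0.05 (Section IV).

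Assumptions: a two-sided test; a 49/49 split; no true difference; normal data on some scale (the Mann–Whitney test depends only on ranks, so any monotone scale will do); and verification that raises the obese group by d SD on that scale.

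Formulas:

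- SE = √(1/n₁ + 1/n₂) = √(1/49 + 1/49) = 0.2020
- Mann–Whitney efficiency factor under normality = √(3/π) = 0.9772
- δ = (d / SE) × 0.9772
- False-positive rate = [1 − Φ(1.96 − δ)] + Φ(−1.96 − δ)

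| Assumed shift d (SD) | δ | Upper tail | Lower tail | Total |
|---|---|---|---|---|
| 0 | 0 | 2.50% | 2.50% | 5.0% |
| 0.1 | 0.484 | 6.99% | 0.73% | 7.7% |
| 0.2 | 0.967 | 16.05% | 0.17% | 16.2% |
| 0.3 | 1.451 | 30.54% | 0.03% | 30.6% |

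The upper tail is a significant result in the hypothesised direction. Nearly all the excess falls there.

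A simulation of the same test (6,000 replicates, 49/49) gave 4.6%, 7.2%, 15.0% and 30.5%, which agrees closely.

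The split is not stated, so an unequal one was tried. With 30:68, SE = √(1/30 + 1/68) = 0.2192, and the formula gives 7.3%, 14.5% and 26.7% for the three shifts. The split matters little; the assumed shift drives the result.

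**The case against.** The strongest reply is that silence is not evidence. A reader might infer that the recordings were verified by someone who knew the BMI group. The document does not support that inference: it says nothing on who verified or what they knew, and verification may have been masked without being reported. This part of the objection stands, and the point is limited to the absence of any described safeguard.

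A second reply is that the software does much of the work and the document does not show that verification changes the DeMeester score. That also stands as a limit on size. Deleting episodes or judging artefact would be natural examples of manual edits, but the document mentions neither. Still, it does state a manual step and does not bound its effect, so the risk cannot be called negligible either.

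Third, the shifts of 0.1 to 0.3 SD are chosen freely, and any bias of that size would give the same rates. This is correct. A reader might take 30% as this study's false-positive risk, which nothing in the document supports.

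Fourth, the text is in the past tense and places the study between January and October 2017. Read literally, masking before the first read is no longer possible. That changes the form of the remedy but does not answer the point.

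Finally, hiatal hernia and erosive esophagitis carry two of the three hypotheses. They too are assessed with no masking described, at an endoscopy where the patient is present. Coding recordings does nothing for those outcomes, but that is no reason to leave the recordings unprotected.

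**Conclusion.** The point holds as a gap in protection, not as a demonstrated bias. As written, the plan leaves the measurements behind its first hypothesis exposed to reader expectation: there is a manual step, the group is established beforehand, the hypothesis is directional, and no masking is described.

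The size is unknown and cannot be derived from the document. Under the stated assumptions, a shift of 0.1 SD would do little harm, 0.2 SD would roughly triple the nominal 5%, and 0.3 SD would raise it about sixfold. These figures are conditional on the shift and say nothing about whether one occurred.

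A reader might also infer that coded files would eliminate the problem at negligible cost. The document gives no cost or staffing information, and a reader who examined the patient may recognise the recording. Coding should be expected to reduce the bias. The change is worth making because the recordings are already digital files and no extra reader or test is needed.

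**What to change.** 1. State in Section III.D that name, weight, height and BMI are removed from each recording and its diary, and that both carry only a study code.
2. Have the existing reader verify the coded recordings without access to BMI group. Ideally this is a reader who did not examine the patient.
3. Lock the verified DeMeester score and acid exposure time before merging them with BMI.
4. If reading is already complete, have the existing reader do a masked re-read of the stored files. If the files were not kept, state the lack of documented masking as a limitation.
5. Where software values from before manual editing are retained, report the group comparison on them as a sensitivity check. A marked difference from the verified result would suggest that the edits drive it.

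The cost is the work of coding files, a short addition to the procedure and a minor delay; a re-read adds reading time. Occasional recognition of a patient remains possible, and hiatal hernia and erosive esophagitis are not covered.

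### The obese versus normal-BMI comparison is planned with unadjusted tests only, so an age or sex difference between the groups could create or hide an association with reflux severity

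*Combined protocol and SAP*

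**What the plan says.** Section III.A gives the design: "This study is a cross sectional study". The groups are formed by BMI cut-offs in the inclusion criteria (III.C). The general objective (II.A) is "To ascertain if there is an association between obesity and severity of esophageal reflux"; the title goes further and speaks of "IMPACT OF OBESITY ON SEVERITY OF ESOPHAGEAL REFLUX".

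Section IV is the whole inferential plan. It contains two tests:

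- For binary findings: "Dichotomous categorical variables were analyzed using the chi-square test".
- For the DeMeester score: "non-normal data was subjected to bivariate analysis using the" Mann–Whitney test between the two groups.

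Descriptive reporting is stated in general terms ("Categorical variables are presented as frequency and percentage"; means or medians for numerical variables), without saying that age and sex will be shown by BMI group. No covariate, regression model, matching or stratification appears anywhere in the document.

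On the data available, III.D states: "All 98 eligible subjects (59 female and 39 male) were recruited, provided anamnesis, and underwent a physical examination". The age criterion in III.C is "Adults, aged 18–60 years".

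**The concern.** Patients are not assigned to a BMI group, so obese and normal-BMI patients may differ in age and sex. If either factor is related to acid reflux, a crude comparison mixes its effect with that of obesity. This can work in both directions: a difference may appear where obesity plays no part, or a real difference may be cancelled.

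The 18–60 limit and the excluded diseases and drugs narrow the population. They still leave a 42-year age span and both sexes, and nothing balances either between the groups. The study's main conclusion rests on this one comparison, and the planned tests cannot separate obesity from the age and sex mix.

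**Working it through.** **Figures in the plan.** There is no sample-size, power or effect-size figure to reproduce. The counts agree: 110 − 12 = 98 and 59 + 39 = 98.

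**Inputs from the document.** n = 98, 39 men, ages 18–60, significance at 0.05 (taken as two-sided).

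**Assumptions.** Groups of 49 and 49; the split of the men; a difference in log score between the sexes of 0.5 or 0.8 residual SD; a 5-year difference in mean age; an age–outcome correlation of 0.2 or 0.3. Age SD is taken from a uniform distribution on 18–60: 42/√12 = 12.1 years, so 5 years is 5/12.1 = 0.41 SD.

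**Size of the spurious shift.** For sex it is (difference in proportion of men) × (sex effect):

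- Men 24/15: 9/49 = 0.184, so 0.184 × 0.5 = 0.09 SD, or 0.184 × 0.8 = 0.15 SD.
- Men 27/12: 15/49 = 0.306, so 0.15 or 0.24 SD.

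For age it is 0.41 × r/√(1 − r²): 0.41 × 0.204 = 0.08 SD for r = 0.2, and 0.41 × 0.314 = 0.13 SD for r = 0.3.

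**False-positive rate with no obesity effect.** Simulation, 40,000 replicates per scenario, outcome on the log scale with residual SD 1. The Mann–Whitney test is unaffected by the log transformation.

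| Scenario (men per group) | Unadjusted, smaller effect | Unadjusted, larger effect |
|---|---|---|
| 20/19, sex effect 0.5 / 0.8 SD | 4.5% | 3.7% |
| 24/15, sex effect 0.5 / 0.8 SD | 6.5% | 8.6% |
| 27/12, sex effect 0.5 / 0.8 SD | 10.2% | 18.6% |
| 5-year age gap only, r = 0.2 / 0.3 | 6.8% | 9.2% |
| 24/15 (0.5 SD) plus the age gap, r = 0.2 / 0.3 | 11.9% | 16.3% |

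A linear model with group, sex and age gives 4.8–5.2% in every one of these scenarios. Unequal groups of 60 and 38 behave alike: men 24/15 (balanced there) give 4.6% or 3.5%, 28/11 give 6.3% or 8.1%, and 31/8 give 10.4% or 17.6%.

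**How likely such splits are by chance.** If sex is unrelated to BMI group, the number of men in one group of 49 is hypergeometric (98 subjects, 39 men). The two-sided probability of a split at least as uneven as 24/15 is 0.098, and as 27/12 it is 0.0036. The 27/12 row therefore presupposes a real link between sex and obesity.

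**Masking.** True obesity effect 0.5 SD, sex effect 0.5 SD:

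| Men, obese / normal BMI | Power, unadjusted | Power, adjusted |
|---|---|---|
| 20/19 | 66% | 68% |
| 15/24 | 47% | 67% |
| 12/27 | 36% | 64% |

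With 15/24, the crude difference shrinks from 0.5 to 0.5 − 0.09 = 0.41 SD.

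**The case against.** The hypotheses in II.C are worded as crude contrasts, and the planned tests answer them. Nothing in the document says that age or sex affects the DeMeester score; the Background names diet, physical activity and genetic predisposition instead, and the proposed models do not cover these. The document shows that age was checked for eligibility but does not say it was kept as an analysis variable. All the imbalances above are assumed. A mild split of 22/17 with a 0.5 SD sex effect gives 4.7%, and averaged over random splits unrelated to BMI the error rate is 4.8–5.0%. The linear model is also favoured, because it matches how the data were generated. Finally, the text is in the past tense, so an adjusted analysis may be post hoc.

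Much of this limits the claim without removing it. The size of any bias is unknown, and inflation beyond chance requires that age or sex be systematically related to BMI group. Adjustment removes two alternative explanations, not all of them. That age is on record is an inference, though a strong one. The general descriptive sentences in Section IV may lead to a table of age and sex, which could reveal an imbalance but would not correct for it.

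The modelling objection is weaker. A rank-based regression on group, sex and age, in a separate simulation of 4,000 runs per scenario, held 4.2–5.2% under the null. With no imbalance and a true 0.6 SD effect it had 80.1% power, against 80.4% for the Mann–Whitney test. The proportional-odds and logistic models were not simulated.

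**Conclusion.** The concern holds. For a non-randomised comparison, the plan relies wholly on crude tests and leaves unused two covariates that should be on file for every subject. Bias is not demonstrated, because neither age nor sex is reported by BMI group. Under the stated assumptions the effect ranges from negligible in balanced groups to a false-positive rate of 19% in the extreme case, with roughly 6–16% for moderate imbalances. A moderate imbalance in the opposite direction costs about 20 percentage points of power. This should be fixed: the remedy is cheap and loses almost no precision if the groups turn out to be balanced.

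**What to change.** In Section IV:

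- Add one named model for the DeMeester score and acid exposure time with BMI group, age and sex as covariates. A proportional-odds model is a natural choice because it accommodates zero acid exposure; a linear model on the log score would need an offset for zeros.
- Add logistic models with the same covariates for hiatal hernia and erosive esophagitis, with a penalised fit if events are few.
- Base the conclusion on the adjusted obesity estimates with 95% confidence intervals, and report the planned unadjusted tests and group summaries beside them.
- Tabulate age and sex by BMI group.
- Do not adjust the DeMeester model for hernia or esophagitis, which may lie on the causal path.
- State that diet, physical activity and genetic predisposition remain unadjusted, and word the conclusions as association and not impact.
- If the data have already been analysed, label the adjusted analysis as added later.

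The cost is some SAP wording and a few lines of Stata code, with no new data provided age was retained. The drawbacks are a modelling assumption to check, event counts that are not yet known for the logistic models, and post hoc status if results have already been seen.
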